9.3	IBC Approval and Reporting	80
9.4	Office of Biotechnology Activities	80
9.5	Protection of Human Subjects	80
9.5.1	Compliance with Informed Consent Regulations	80
9.5.2	Compliance with IRB/EC Requirements	80
9.5.3	Compliance with Good Clinical Practice	80
9.5.4	Compliance with Electronic Records/Signature Regulations (21CFR Part 11)	80
9.5.5	Compliance with Protocol	80
9.5.6	Changes to the Protocol.....	80
10.0	DATA COLLECTION, MONITORING, AND REPORTING	81
10.1	Confidentiality and Privacy	81
11.0	SOURCE DOCUMENTS	81
11.1	Records Retention	82
12.0	SAFETY AND QUALITY MONITORING.....	82
12.1	Safety and Quality Monitoring.....	82
12.2	Pathology Adjudication Committee	82
12.3	Clinical Monitoring.....	82
13.0	PUBLICATION POLICY.....	83
14.0	LIST OF ABBREVIATIONS	83
15.0	REFERENCES.....	86
16.0	APPENDICES.....	88

CLINICAL PROTOCOL SYNOPSIS

Protocol Title: A Phase 2, Open Label, Study of VGX-3100 Delivered Intramuscularly (IM) Followed by Electroporation (EP) for the Treatment of HPV-16 and/or HPV-18 related Anal or Anal/Peri-anal High-Grade Squamous Intraepithelial Lesions, HSIL (AIN2, AIN3, PAIN2, PAIN3) in individuals that are seronegative for Human Immunodeficiency Virus (HIV)-1/2
Protocol Number: HPV-203
Trial Phase: 2a
Estimated Number of Trial Centers and Countries/Regions: Approximately 3 study centers located in North America
Formulation: VGX-3100
Trial Design: Multi-center, single-arm, open-label phase 2 study
Criteria for Evaluation: To provide a treatment to regress anal or anal/peri-anal HSIL and clear the related HPV-16 and/or HPV-18 (HPV16/18) in individuals that are seronegative for HIV-1/2.
Research Hypothesis: VGX-3100 followed by electroporation (EP) administered to adults with histologically confirmed anal or anal/peri-anal HSIL ¹ , (AIN2 ² , AIN3 ³ , PAIN2 ⁴ , PAIN3 ⁵) associated with HPV-16 and/or HPV-18 will result in a higher proportion with histopathologic regression of intra-anal and/or peri-anal HSIL lesions to no evidence of anal or anal/peri-anal HSIL and virologic clearance of HPV-16 and/or 18 than historical controls.
Dose of VGX-3100: 6 mg (1mL)
Administration: Intramuscular injection followed by EP
VGX-3100 Dosing Schedule: Day 0, Week 4 and Week 12 with one additional dose given to partial responders at Week 40
Study Duration: 88 Weeks
Primary Objective: Determine the efficacy of 3 doses of VGX-3100 with respect to combined histopathologic regression of anal or anal/peri-anal HSIL and virologic clearance of HPV-16 and/or HPV-18.
Primary Endpoint: Proportion of subjects with no histologic evidence of anal or anal/peri-anal HSIL ⁶ on histology (i.e., collected via biopsy or excisional treatment) ⁷ and no evidence of HPV-16/18 at Week 36 from intra-anal and/or peri-anal lesion tissue ⁸ .

¹ High-grade Squamous Intraepithelial Lesion

² Grade 2 Anal Intraepithelial Neoplasia

³ Grade 3 Anal Intraepithelial Neoplasia

⁴ Grade 2 Peri-anal Intraepithelial Neoplasia

⁵ Grade 3 Peri-anal Intraepithelial Neoplasia

⁶ No evidence of anal or anal/peri-anal HSIL is defined as normal tissue or anal or anal/peri-anal LSIL.

⁷ A treatment responder is defined as a subject with no histologic evidence of anal or anal/peri-anal HSIL and no evidence of HPV-16 or HPV-18 in anal lesion tissue and who did not receive any non-study treatment of curative intent of intra-anal and/or peri-anal lesions. A treatment non-responder is defined as a subject with histologic evidence of anal or anal/peri-anal HSIL, adenocarcinoma-in-situ (AIS), anal or anal/peri-anal carcinoma or a subject with evidence of HPV-16/18 in anal lesion tissue or a subject who received non-study treatment of curative intent of intra-anal and/or peri-anal lesions.

⁸ An intra-anal and/or peri-anal lesion evaluated by the Pathology Adjudication Committee (PAC).

Secondary Objectives	Associated Secondary Endpoints
1. Evaluate the safety and tolerability of VGX-3100 delivered IM followed by EP	1a. Local and systemic events for 7 days following each dose as noted in the Participant Diary Card (PDC). 1b. All adverse events including SAEs, UADEs, and other unexpected AEs for the duration of the study (through the Week 88 visit)
2. Determine the efficacy of three doses of VGX-3100, as measured by histologic regression of anal or anal/peri-anal HSIL	2. Proportion of subjects with no evidence of anal or anal/peri-anal HSIL on histology (e.g. biopsies or excisional treatment) at Week 36
3. Determine the efficacy of three doses of VGX-3100 as measured by virologic clearance of HPV-16 and/or HPV-18 by testing from lesion tissue	3. Proportion of subjects with no evidence of HPV-16 and/or HPV-18 ⁹ from intra-anal and/or peri-anal tissue by type specific HPV testing at Week 36
4. Determine the efficacy of three doses of VGX-3100 as measured by virologic clearance of HPV-16 and/or HPV-18 by intra-anal swab testing	4. Proportion of subjects with no evidence of HPV-16 and/or HPV-18 from intra-anal swab by specific HPV testing at Week 36
5. Determine the efficacy of three doses of VGX-3100 as measured by complete histopathologic regression of anal or anal/peri-anal HSIL to normal tissue	5. Proportion of subjects with no evidence ¹⁰ of anal or anal/peri-anal Low grade squamous intraepithelial lesion (LSIL) or HSIL (i.e. no evidence of AIN2, AIN3, PAIN2, PAIN3) on histology (i.e. biopsies or excisional treatment) at Week 36
6. Determine the efficacy of three doses of VGX-3100 as measured by histopathologic non-progression of anal or anal/peri-anal HSIL	6. Proportion of subjects with no progression ¹¹ of anal or anal/peri-anal HSIL to carcinoma from baseline to histology (i.e. biopsies or excisional treatment) at Week 36
7. Describe the efficacy of VGX-3100 for partial responders , as measured by reduction in the number of intra-anal and/or peri-anal qualifying lesion(s), as applicable and the reduction in size of peri-anal lesion(s) if present, and for whom the disease has not progressed according to Investigator judgment in subjects who did not have anal or anal/peri-anal HSIL lesion resolution at Week 36	7. Percent reduction in the number of qualifying ¹² intra-anal and/or peri-anal lesion(s), and the reduction in size of peri-anal lesion(s) as determined by the Investigator at Weeks 36, 64, and 88 compared to baseline ¹³ .
8. Determine the cellular immune response following dose 3 and compared to baseline	8. Flow Cytometry response magnitude at baseline and Week 15

9. Determine the efficacy of three doses of VGX-3100 with respect to histopathologic regression of anal or anal/peri-anal HSIL or virologic clearance of HPV-16 and/or HPV-18
	
9. Proportion of subjects with no histologic evidence of anal or anal/peri-anal HSIL by histology (i.e., collected via biopsy or excisional treatment) or no evidence of HPV-16/18 at Week 36 from intra-anal and/or peri-anal lesion tissue

---	---

⁹ Clearance of HPV-16 or HPV-18 is defined as being undetectable by PCR assay.

¹⁰ No evidence of anal or anal/peri-anal HSIL is defined as normal tissue or anal or anal/peri-anal LSIL.

¹¹ Progression is defined as advancement to carcinoma by histology according to the Pathology Adjudication Committee.

¹² An intra-anal and/or peri-anal lesion which is confirmed to be HPV-16 and/or HPV-18 positive and have histologically confirmed anal or anal/peri-anal HSIL evaluated by the Pathology Adjudication Committee (PAC).

¹³ Baseline photographic imaging is defined as photographs obtained pre-biopsy at Screening, or post biopsy at Screening (for subjects with historical biopsy tissue).

Exploratory Objectives	Associated Exploratory Endpoints
1. Describe the long term efficacy of VGX-3100 with respect to combined histopathologic regression of anal or anal/peri-anal HSIL and virologic clearance of HPV-16 and/or HPV-18	1. Proportion of subjects with no histologic evidence of anal or anal/peri-anal HSIL on histology (i.e. collected via biopsy or excisional treatment) and no evidence of HPV-16/18 at Week 64 by testing from intra-anal and/or peri-anal lesion tissue
2. Describe the long term efficacy of VGX-3100, as measured by histologic regression of anal or anal/peri-anal HSIL	2. Proportion of subjects with no evidence of anal or anal/peri-anal HSIL on histology (i.e. biopsies or excisional treatment) at Week 64
3. Describe the long term efficacy of VGX-3100, as measured by virologic clearance of HPV-16 and/or HPV-18 by testing from lesion tissue	3. Proportion of subjects with no HPV-16/18 at Week 64 by testing from intra-anal and/or peri-anal lesion tissue
4. Describe the long term efficacy of VGX-3100, as measured by virologic clearance of HPV-16 and/or HPV-18 by intra-anal swab testing	4. Proportion of subjects with no evidence of HPV-16 and/or HPV-18 from intra-anal swab by specific HPV testing at Week 64 and Week 88
5. Evaluate tissue immune responses to VGX-3100 in intra-anal and/or peri-anal samples	5. Assessment of proinflammatory and immunosuppressive elements in tissue, where feasible ¹⁴
6. Describe the clearance of HPV-16 and/or HPV-18 infection from non-anal anatomic locations	6. Proportion of subjects who have cleared HPV-16 and/or HPV-18 on specimens from non-anal anatomic locations as applicable based upon gender (i.e. oropharynx, cervical, vaginal, and penile at Week 36)
7. Describe the association of microRNA (miRNA) profile, previous anoscopy, cytology and HPV testing results with Week 36 histologic regression	7. HRA, cytology, and HPV test results and miRNA profile (baseline and at the Weeks 15 and 36) in conjunction with histologic regression of anal or anal/peri-anal HSIL at Week 36
8. Describe patient reported outcomes (PRO) for subjects treated with VGX-3100	8. Patient reported outcome (PRO) endpoints prior to first dose (Day 0), on the day of and following each dose, and at Weeks 36, 64, and 88. There will be an

	additional PRO assessment at Week 40 if a subject receives a 4 th dose
9. Determine the humoral and cellular immune response following dose 3 and additional time points compared to baseline	9a. Levels of serum anti-HPV-16 and anti-HPV-18 antibody concentrations at baseline and Weeks 15, 36, and 88 9b. Interferon- γ ELISpot response spot forming units (SFU) at baseline and Weeks 15, 36, and 88
10. Determine the long term efficacy of VGX-3100 with respect to histopathologic regression of anal or anal/peri-anal HSIL or virologic clearance of HPV-16 and/or HPV-18	10. Proportion of subjects with no histologic evidence of anal or anal/peri-anal HSIL on histology (i.e., collected via biopsy or excisional treatment) or no evidence of HPV-16 and/or HPV-18 at Week 64 from intra-anal and/or peri-anal lesion

¹⁴ Additional assessments may include visualization of PD-L1, Granulysin, Perforin, CD137, CD103 and possible other relevant markers identified in the literature as sample allows.

[figure not shown]
Study Design:

HPV-203 is a Phase 2, open-label efficacy study of VGX-3100 (DNA plasmids encoding E6 and E7 proteins of HPV types 16 and 18) administered by IM injection followed by EP in adult men and women who are HIV negative with histologically confirmed anal or anal/peri-anal HSIL associated with HPV-16 and/or HPV-18.

Approximately 24 subjects will receive at least 3 doses of VGX-3100. Each dose of VGX-3100 will be administered in a 1 mL volume IM followed immediately by EP. As shown in **Figure 1**, study subjects will receive at least 3 doses of VGX-3100 depending upon their disposition with regard to histologic and lesion area changes during the trial. The first dose will be administered on Day 0, the second at Week 4, and the third at Week 12. Partial response to VGX-3100 may still be of medical importance by being able to limit the extent of surgery necessary. For partial responders at Week 36, a fourth dose may be administered at Week 40.

All subjects are scheduled to be followed to Week 88.

Figure 1: HPV-203 Study Visit Schedule

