Pre-biopsy High Resolution Anoscopy Finding	Minimally required procedure
No lesion	Punch biopsy and photography; biopsy should be collected from within the approximate original boundaries of the study entry HSIL as proximal as possible to the original biopsy site which was previously determined to be HSIL by the PAC. New lesions or lesions that did not qualify at baseline should be biopsied at evaluation.
Single lesion (which was also present at baseline)	Punch biopsy and photography; biopsy should be collected within the boundaries of the original lesion and from the area most suspicious for advanced disease within the lesion by clinical exam. New lesions or lesions that did not qualify at baseline should be biopsied at evaluation.
Multiple lesions	Punch biopsies and photography; biopsy should be collected from the same lesions diagnosed as HSIL from study entry and from the area most suspicious for advanced disease within the lesion by clinical exam. New lesions or lesions that did not qualify at baseline should be biopsied at evaluation.

If HSIL is diagnosed in any Week 36 biopsy, but there is a reduction in the number of intra-anal and/or peri-anal lesion(s), reduction in peri-anal lesion(s) size or no change in peri-anal lesion(s) size from baseline (defined by Subgroup C), the Investigator has the option to administer a 4th dose of VGX-3100 at Week 40, and the subject will continue on the study to have HRA and biopsy at Week 64 of all lesions (qualifying and any other visible), i.e. the second efficacy checkpoint. Alternatively, the Investigator may instead choose to treat the subject with standard of care treatment (i.e. electrocautery, ablation, surgical excision), and the subject will continue on the study without further biopsy unless it is part of standard of care.

In the event of worsening anal or anal/peri-anal HSIL at any time during the trial (defined as any increase in lesion(s) area from baseline or worsening of anal or anal/peri-anal HSIL to cancer), the subject may receive standard of care treatment (i.e. electrocautery, ablation, surgical excision) per the Investigator's judgment but will continue on the study through Week 88 with HRA, but without further biopsy unless it is part of the standard of care.

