Intra-anal and/or peri-anal swabs will be collected at Screening, Day 0, and at Weeks 4, 15, 28, 36, 64 and 88 as a less invasive measure for exploratory purposes to determine the presence of HPV-16 and/or -18 as well as other high risk HPV types using HPV testing. Similarly, vaginal, cervical (female subjects), penile (male subjects), and oropharyngeal (OP) rinse samples will be obtained at Day 0, and Weeks 4, 15, 28, 36, 64, and 88 to assess systemic virologic response to treatment.

If after evaluation of the biopsy tissue at Week 36, HSIL remains, but there is a reduction in intra-anal and/or peri-anal lesion(s) number and no increase in peri-anal lesion(s) size from baseline (Subgroup C), the Investigator will have the option to administer a 4th dose of VGX-3100 at Week 40 and the subject will continue on the study with HRA and biopsy at Week 64. Alternatively, the Investigator may choose to treat the subject with standard of care treatment (i.e. electrocautery, ablation, surgical excision), and the subject will continue on the study without further biopsy. If HSIL remains based on the Week 64 biopsy results, the subject will receive standard of care and remain on the study for safety and follow up only.

Immunogenicity Assessment: Humoral and cell mediated immune responses to VGX-3100 may be evaluated in blood samples taken at baseline (both Screening as well as Day 0 prior to dosing) and at Weeks 15, 36, and 88. Intra-anal and/or peri-anal tissue samples may also be analyzed for evidence of proinflammatory and immunosuppressive elements at Week 36 as compared to baseline (Screening), where feasible.

Virologic Assessment: Intra-anal and/or peri-anal swabs will be obtained to characterize HPV infection at Screening, Day 0, and Weeks 4, 15, 28, 36, 64 and 88. Likewise, PCR-based assessment of histological samples will occur at Screening and Weeks 36 and 64.

For testing of non-anal sites, vaginal, cervical (female subjects), penile (male subjects), and oropharyngeal (OP) samples (all subjects) will be obtained to characterize HPV infection at Day 0, and at Weeks 4, 15, 28, 36, 64 and 88.

Safety Assessment: Subjects will be monitored for:

- 1) Local and systemic events for 7 days following each VGX-3100 dose as noted in the Participant Diary Card (PCD).
- 2) All adverse events including SAEs, UADEs, and other unexpected AEs for the duration of the study.

All subjects will be followed to Week 88.

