3.3 SECONDARY OBJECTIVE(S)

- Evaluate the **safety** and **tolerability** of VGX-3100 delivered IM followed by EP
- Determine the **efficacy** of three doses of VGX-3100 as measured by **histologic regression** of anal or anal/peri-anal HSIL
- Determine the **efficacy** of three doses of VGX-3100 as measured by **virologic clearance** of HPV-16 and/or HPV-18 by testing from lesion tissue
- Determine the **efficacy** of three doses VGX-3100 as measured by **virologic clearance** of HPV-16 and/or HPV-18 by intra-anal swab testing
- Determine the **efficacy** of three doses of VGX-3100 as measured by **complete histopathologic regression** of anal or anal/peri-anal HSIL to normal tissue
- Determine the **efficacy** of three doses of VGX-3100 as measured by **histopathologic non-progression** of anal or anal/peri-anal HSIL
- Describe the **efficacy** of VGX-3100 for **partial responders**, as measured by reduction in the number of intra-anal and/or peri-anal lesion(s), as applicable **and** the reduction in the size of peri-anal qualifying lesion(s), if present, **and** for whom the disease has not progressed according to Investigator judgment in subjects who did not have anal or anal/peri-anal HSIL lesion resolution at Week 36
- Determine the cellular immune response following administration of VGX-3100 at post dose 3, and after additional dosing compared to baseline

- Determine the **efficacy** of three doses of VGX-3100 with respect to histopathological regression of anal or anal/peri-anal HSIL or virologic clearance of HPV-16 and/or HPV-18

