8.5.2 SECONDARY ANALYSES

The secondary efficacy binary endpoints will be analyzed in the same manner as the primary hypothesis, but without the hypothesis test p-values. The efficacy time frame is defined in the same manner as for the primary endpoint. All of the efficacy binary endpoints will be analyzed in two ways: a) based on all lesions and b) based on qualifying and new lesions.

The anatomic extent endpoint will be analyzed by calculating the mean percent change in surface area and the mean percent change in number of lesions and associated 95% t-distribution based confidence intervals.

Post-baseline increases in Flow responses will be summarized with medians and 95% CIs. Valid samples for statistical analysis purposes will be those collected within 14 days of the specified visits. Baseline is defined as the last measurement prior to the first treatment administration.

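### Secondary Objective 7 restricts the lesion number and size result to partial responders, a group selected on those same Week 36 measurements, while Endpoint 7 and Section 8.5.2 name no population

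*Protocol*

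**What the plan says.** All references are to protocol Version 3.0.

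- **Objective 7** (synopsis; Section 3.3) describes efficacy in partial responders through reduction in lesion number and in peri-anal lesion size. Judged at Week 36, the group is limited to those "for whom the disease has not progressed according to Investigator judgment in subjects who did not have anal or anal/peri-anal HSIL lesion resolution".
- **Endpoint 7** (synopsis; Section 3.4) is the percent reduction in the number of qualifying lesions "and the reduction in size of peri-anal lesion(s) as determined by the Investigator at Weeks 36, 64, and 88 compared to baseline". It names no subgroup.
- **Section 8.5.2** plans "calculating the mean percent change in surface area and the mean percent change in number of lesions and associated 95% t-distribution based confidence intervals". It names no population.
- **Section 8.4** makes mITT, all subjects with at least one dose, primary for efficacy.
- **Subgroup C**, the operational form of partial response, is worded in two ways. The synopsis study-design text lists fewer lesions, smaller peri-anal size or unchanged peri-anal size. The synopsis efficacy-assessment text and Section 3.7 require fewer lesions and "no increase in peri-anal lesion(s) size from baseline (Subgroup C").
- **Progression** is carcinoma on committee histology in synopsis footnote 11, but Objective 7 relies on Investigator judgment. Separately, the study-design text has worsening "defined as any increase in lesion(s) area from baseline" or to cancer.

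**The concern.** The objective picks subjects because their lesions shrank, or did not grow, by Week 36, and the endpoint then averages the Week 36 shrinkage in those subjects. Increases are left out before the mean is taken. The trial has one arm, so a reader will compare an interval for change from baseline with zero. An interval below zero would look like drug effect when selection alone can produce it. An analyst following Section 8.4 would include everyone and get a different answer. Section 8.1 presents Section 8 as the formal statistical analysis plan, so the conflict is not visibly left for another document to settle.

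**Working it through.** **Inputs from the protocol.** 24 subjects, 90% evaluable at Week 36, 15% historical response (Section 8.6); about 20% spontaneous regression by one year (Section 1.1).

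**Assumed, because the protocol gives no figure.** Spread of percent change, number of partial responders, share with peri-anal lesions, share unchanged, and correlation between visits. Ranges are shown.

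**1. The plan's own figure.** The protocol gives no precision figure for this endpoint. Its one planning figure, about 80% power for the primary test, reproduces. Evaluable subjects are 24 × 0.9 = 21.6. The exact one-sided 0.05 test of 15% against 40% rejects at 7 or more responders, with power 0.800 at n = 21 and 0.842 at n = 22. I use 22 below.

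**2. Sign of the mean.** If every selected subject has change ≤ 0, the mean is ≤ 0, whatever the product does. For an inactive product with change distributed Normal(0, SD), keeping only reductions gives an expected mean of −SD × √(2/π):
- SD 20: −0.798 × 20 = −16 points
- SD 40: −0.798 × 40 = −32 points

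**3. The interval at a fixed number selected.** Upper limit = mean + t(0.975, n−1) × s/√n. Inactive product, 100,000 simulated groups per cell:

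| Selected n | Only reduced subjects: P(interval below 0) | Unchanged admitted (assumed 4/7 of group) |
|---|---|---|
| 2 | 0.10 | 0.02 |
| 3 | 0.20 | 0.02 |
| 4 | 0.40 | 0.01 |
| 5 | 0.66 | 0.04 |
| 6 | 0.85 | 0.07 |
| 8 | 0.98 | 0.17 |
| 10 | at least 0.998 | 0.31 |

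Without selection the probability is 0.024 to 0.026.

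Exclusion of zero is not automatic. Changes of −10, −20 and −90 have mean −40 and s = 43.6, so the half-width is 4.303 × 43.6/√3 = 108 and the interval runs from −148 to +68.

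**4. Whole trials, inactive product.**
- Model A: mean-zero log-normal change with log-SD 0.1 to 0.5; 20% resolved and removed; increases removed. With 22 measurable subjects, about 9 to 10.5 are selected, the mean is about −8% to −33%, and the interval is below zero in 96% to over 99% of trials. With 11 measurable subjects (half with peri-anal lesions, say), about 5 are selected and the figure is about 56% to 78%.
- Model B: 22 evaluable, 85% unresolved, SD 30. If 20%, 30% or 50% of unresolved subjects shrink by chance, the average number selected is 3.7, 5.6 or 9.3 and the probability is 0.43, 0.69 or 0.96.

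**5. Weeks 64 and 88, selected on Week 36 (SD 30).** Expected mean = −ρ × 30 × 0.798, where ρ is the correlation with Week 36:
- ρ = 0: mean 0, probability 0.025
- ρ = 0.5: mean −12, probability 0.09 to 0.23 for n = 4 to 10
- ρ = 0.8: mean −19, probability 0.20 to 0.66 for n = 4 to 10

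**6. What mITT does and does not repair.** With a mean-zero change in everyone, the interval behaves nominally (step 3). If resolved subjects are counted as −100% (an assumption), the mITT mean for an inactive product is 0.20 × (−100) = −20%, and under Model A the interval lies below zero in about 35% to 58% of trials at n = 22. Lesion number has a further problem. If qualifying status is fixed at Screening, that count cannot exceed baseline even in mITT. With an assumed 1 to 3 lesions per subject and 15% to 29% spontaneous clearance per lesion, the interval is below zero in 0.66 to 0.99 of trials at n = 22.

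**The case against.** The strongest reply is that no subgroup analysis is actually prescribed. The restriction sits in the objective only. Section 8.2 lists anatomic extent among the secondary efficacy analyses, and Section 8.4 makes mITT primary for efficacy, so mITT is a fair default reading. That stands: the text is in conflict, and one cannot say that the endpoint is assigned to partial responders. The conflict still needs settling, because the objective states its group explicitly.

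Three further replies also stand in part:

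- **The selection rule is loose.** Footnote 11 makes progression a carcinoma finding, so the no-progression clause does not by itself remove growth. The area-increase wording governs optional standard-of-care treatment, not an analysis set. One Subgroup C wording admits unchanged size. If its list is read as alternatives, a subject could enter on one measure while the other rises. The guaranteed sign therefore rests on the partial-responder wording and on the measure used to select.
- **Only peri-anal lesions are sized by ruler**, so the number entering the size mean may be small.
- **No test is planned.** The objective says that it describes, and Section 8.3 confines formal hypotheses to the primary endpoint. How far lesions shrank in partial responders is a fair descriptive question. But the objective calls the result efficacy, and an interval around a mean change invites comparison with zero.

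**Conclusion.** The point holds as a conflict over population with a real consequence. Under Objective 7, the Week 36 mean percent change cannot be positive, whatever the product does. With about 5 to 10 selected subjects and the assumed variability, the 95% interval lies wholly below zero in roughly 55% to 99% of null trials, against 2.5% nominal. It does so in 40% or fewer at a fixed n of four or below, and in 7% to 31% at n = 6 to 10 when unchanged subjects make up an assumed 4/7 of the group.

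Three stronger readings are tempting, and the documents do not support them:

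- **The interval excludes zero by construction.** Only the sign of the mean is fixed. The interval depends on how many subjects are selected and on their spread.
- **Weeks 64 and 88 inherit the full bias.** It is attenuated and vanishes if later values are uncorrelated with Week 36.
- **Moving to mITT restores a nominal interval around zero.** It removes selection on the outcome, but spontaneous regression remains in a single-arm change from baseline.

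This is a descriptive secondary endpoint, and the primary conclusion is untouched. The correction is still worth making before the result is reported as efficacy.

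**What to change.** 1. In Objective 7 and Section 8.5.2, name one population: all mITT subjects with a baseline measurement, whatever the direction of change. For peri-anal size, use those with peri-anal lesions at baseline. Compute the mean percent change and its interval there.
2. Count new lesions as well as qualifying ones, so that lesion number can rise.
3. Report partial responders as a count and a proportion of mITT. Keep any summary of change within that group descriptive, without a confidence interval.
4. Reconcile the Subgroup C wordings in the synopsis study-design text, the synopsis efficacy-assessment text and Section 3.7. Which one is intended is for the sponsor to state.
5. Add that the mITT change from baseline in a single arm includes spontaneous regression and is not by itself evidence of efficacy.

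Cost: a few sentences and no new visits, since anoscopy is scheduled for every subject at Weeks 36, 64 and 88. The reported mean will change and will no longer isolate partial responders.
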